6.6 Medical Devices

Medical devices (eg, sterile needles, alcohol prep pads) that are commercially available are not usually provided or reimbursed by the Sponsor (except, for example, if required by local regulation). The investigator will be responsible for obtaining supplies of these devices.

6.7 Product Complaints

A product complaint is any written, electronic or oral communication that alleges deficiencies related to the identity, quality, durability, reliability, safety, effectiveness, or performance of a drug(s) or device(s) after it is released for distribution to market or

clinic by either Amgen or by distributors and partners for whom Amgen manufactures the material.

This includes any drug(s) or device(s) provisioned and/or repackaged/modified by Amgen. Drug(s) or device(s) includes investigational product.

Any product complaint(s) associated with an investigational product(s) or non-investigational product(s) supplied by Amgen are to be reported according to the instructions provided in the IPIM.

6.8 Excluded Treatments, Medical Devices, and/or Procedures During Study Period

Subjects must not use any of the following therapies during screening or treatment period:

- other investigational agents or procedures
- concurrent experimental or approved anti-tumor therapies other than study drugs and radiation therapy required for palliation (as noted in [Section 6.5](#)).
- chronic oral or systemic steroid medication use at a dose of > 10 mg/day of prednisone or equivalent (with the exception of treatment for adverse events [see [Section 6.2.1.2](#)] and CNS metastases [see [Section 6.5](#)]). Steroids with low systemic absorption [eg, triamcinolone hexacetonide] injected into a joint space is allowed)
- antiherpetic drugs (eg, acyclovir), other than if topically administered > 20 cm from a talimogene laherparepvec injection site. If a subject requires treatment with a systemic antiherpetic drugs (eg, acyclovir, valacyclovir, famciclovir) talimogene laherparepvec should be withheld and the investigator or designee should notify the Amgen medical monitor as soon as possible. Subject may be allowed to continue treatment after discussion between the Amgen medical monitor and the investigator to determine the appropriateness of treatment resumption.
- Subjects must not schedule any elective surgeries during the treatment period and for at least 30 days after the last administration of study drug. If a subject undergoes any unexpected surgery during the course of the study, study treatment must be withheld and the investigator or designee should notify the sponsor medical monitor as soon as possible. A subject may be allowed to resume study drug if both the investigator and sponsor medical monitor agree to restart study therapy.

6.9 Contraceptive Requirements

A female is considered fertile following menarche and until becoming post-menopausal unless permanently sterile. Permanent sterilization methods include hysterectomy, bilateral salpingectomy, and bilateral oophorectomy.

Female in the following categories are not considered of child bearing potential:

1. Premenopausal female with 1 of the following:
 - a. Documented hysterectomy

- b. Documented bilateral salpingectomy
- c. Documented bilateral oophorectomy

Note: Site personnel documentation from the following sources is acceptable:
1) review of subject medical records, 2) subject medical examination, or 3) subject medical history interview.

- 2. Premenarchal female
- 3. Postmenopausal female
 - a. A postmenopausal state is defined as no menses for 12 months without an alternative medical cause. A high follicle stimulating hormone (FSH) level in the postmenopausal range may be used to confirm a postmenopausal state in women not using hormonal contraception or hormonal replacement therapy (HRT). However, in the absence of 12 months of amenorrhea, a single FSH measurement is insufficient.
 - b. Females on HRT and whose menopausal status is in doubt will be required to use 1 of the non-hormonal highly effective contraception methods if they wish to continue their HRT during the study. Otherwise, they must discontinue HRT to allow confirmation of postmenopausal status before study enrollment.

The naturally occurring herpes simplex virus (HSV-1) can be transmitted through sexual contact. It is not known if talimogene laherparepvec will behave the same way, thus you or your partner should use a latex condom during treatment and for up to 30 days after your last dose when engaging in sexual activity to prevent possible transmission of talimogene laherparepvec. For those with latex allergies, polyurethane condoms may be used.

6.9.1 Female Subject

Female subjects of childbearing potential must agree to use 1 acceptable method of effective contraception (as described in the table below) during treatment and for an additional 3 months after the last dose of talimogene laherparepvec.

Acceptable Methods of Effective Contraception for Female Subjects

• Combined (estrogen and progestogen) or Progestogen-only hormonal methods given orally• Intrauterine device (IUD)• Intrauterine hormonal-releasing system (IUS)• Bilateral tubal ligation• Vasectomized partner (Provided that partner is the sole sexual partner of the female subject of childbearing potential and that the vasectomized partner has received medical assessment of the surgical success)• Sexual abstinence (Defined as refraining from heterosexual intercourse during the entire period of risk associated with the study treatments. The reliability of sexual abstinence must be evaluated in relation to the duration of the trial and the preferred and usual lifestyle of the subject.)• Double barrier method: the male uses a condom and the female may choose either a cap, diaphragm, or sponge with spermicide. (A female condom is not an option due to the risk of tearing when both partners use a condom.)

If a female subject is suspected of being pregnant, the talimogene laherparepvec must be stopped immediately and may not be resumed until absence of pregnancy has been medically confirmed.

6.9.2 Male Subjects

If the male's sole sexual partner is of non-childbearing potential or has had a bilateral tubal ligation, he is not required to use additional forms of contraception during the study. The definition of non-childbearing potential is provided above.

Male subjects with a partner of childbearing potential must agree to not father a child during treatment and for an additional 30 days after the last dose of talimogene laherparepvec.

Contraceptive options for male subjects include:

- Sexual abstinence (defined as refraining from heterosexual intercourse during the entire period of risk associated with talimogene laherparepvec). The reliability of sexual abstinence must be evaluated in relation to the duration of the trial and the preferred and usual lifestyle of the subject. or
- Use a latex condom during treatment and for an additional 30 days after the last dose of talimogene laherparepvec. For those with latex allergies, polyurethane condoms may be used.

The female partner is to use an acceptable method of effective contraception such as: hormonal, IUD, IUS, female barrier method (diaphragm, cervical cap, contraceptive sponge [a female condom is not an option because there is a risk of tearing when both partners use a condom]). Male subjects must not donate sperm during treatment and for an additional 30 days after the last dose of talimogene laherparepvec.

Male subjects with a pregnant partner must practice sexual abstinence or wear a latex condom to prevent exposure of the unborn child to talimogene laherparepvec. For those with latex allergies, polyurethane condoms may be used.

6.9.3 Unacceptable Methods of Birth Control for Male and Female Subjects

Birth control methods that are considered unacceptable in clinical trials include: periodic abstinence (calendar, symptothermal, post-ovulation methods), withdrawal (coitus interruptus), spermicides only, and lactational amenorrhoea method.

Male and female subjects of childbearing potential must receive pregnancy prevention counseling and be advised of the risk to fetus if they become pregnant or father a child during treatment and for 3 months after the last dose of talimogene laherparepvec.

Additional medications given during the study may alter the contraceptive requirements. These additional medications may require female subjects to use highly effective methods of contraception and for an increased length of time. In addition, male subjects may also be required to use contraception. The investigator must discuss these contraceptive changes with the subject.

7. STUDY PROCEDURES

7.1 Schedule of Assessments

For Schedule of Assessments refer to [Table 2](#) .

Table 2. Schedule of Assessments

Week	Screening	Treatment Period ^a									Follow-up Period	
		0 (day 1)	3	5	7	9	11	13	15	15 and beyond	Safety follow-up	Long-term follow-up ^b
GENERAL & SAFETY ASSESSMENTS												
Informed Consent	X											
Demographics	X											
Review of Medical History and Prior Cancer Therapy	X											
Review of Eligibility Criteria	X											
Recording of Concomitant Medications	X	X	X	X	X	X	X	X	X	X	X	
Review of Adverse events, Serious Adverse Events and Disease Related Events	X	X	X	X	X	X	X	X	X	X	X	X
Physical Exam	X	X					X ^b			Every 12 weeks ^b	X	
Vital Signs	X	X	X		X		X		X	Every 4 weeks	X	
Weight			X				X			Every 12 weeks	X	
Height			X									
12-lead ECG	X											
BRAF status, if known ^b	X											
ECOG Performance Status	X	X					X ^b			Every 12 weeks ^b	X	X ^b
Survival Assessment												X
Reporting exposure of caregiver, close contact or health care provider		X	X	X	X	X	X	X	X	X	X	
Reporting of pregnancy or lactation		X	X	X	X	X	X	X	X	X	X	X

Page 1 of 2

Footnotes defined on last page of the table

Table 2. Schedule of Assessments

Week	Screening	Treatment Period ^a									Follow-up Period	
		0 (day 1)	3	5	7	9	11	13	15	15 and beyond	Safety follow-up	Long-term follow-up ^e
LOCAL LABORATORY ASSESSMENTS												
Urine or Serum Pregnancy Test ^c	X										X	
Hematology ^d	X	X	X	X				X		Every 8 weeks	X	
Chemistry ^d	X	X	X	X				X		Every 8 weeks	X	
Serum LDH	X											
PT (or INR) and aPTT	X											
Blood for viral hepatitis testing ^f	X											
DOSING												
Talimogene Laherparepvec		X	X	X	X	X	X	X	X	Every 2 weeks		
TUMOR ASSESSMENTS												
Clinical tumor assessment	X						X ^h			Every 12 weeks ^h	X ^g	X ^g
Radiological tumor assessment	X						X ^h			Every 12 weeks ^h	X ^g	X ^g
CENTRAL LABORATORY ASSESSMENTS												
Swab of Herpetic Lesion for qPCR		Within 3 days of occurrence of suspected lesion of herpetic origin								X	X ^g	
Blood for HSV-1 Antibody Serostatus		Within 3 days prior to dose at day 1 (week 0) and then at week 5										

Page 2 of 2

Footnotes defined on last page of the table

ECOG = Eastern Cooperative Oncology Group; ECG = electrocardiogram; PT = prothrombin time; INR = international normalization ratio; aPTT = activated partial thromboplastin time; qPCR = real-time polymerase chain reaction; BRAF = serine/threonine protein kinase B-Raf V600; LDH = lactate dehydrogenase; PDr = clinically relevant disease progression; WHO = World Health Organization

^a During the treatment period assessments and procedures can be performed \pm 3 days of the planned visit.

^b BRAF V600E/K tumor status result, obtained from a local laboratory prior to screening for this study will be acceptable

^c Urine or serum pregnancy test must be performed on females of childbearing potential within 3 days prior to enrollment and at the safety follow-up visit.

^d Blood samples for hematology and chemistry will be collected at screening, within 3 days prior to talimogene laherparepvec administration on day 1 (week 0), week 3, week 5, week 13 and then every 8 weeks until end of treatment, and at the safety follow-up visit.

^e For subjects that discontinue talimogene laherparepvec for reason other than disease progression or death, the following additional procedures will be conducted during the long-term follow-up: radiographic tumor imaging, clinical tumor assessments, ECOG Performance Status assessments, reporting of pregnancy or lactation, assessment of swabs of lesions of suspected herpetic origin for presence of talimogene laherparepvec DNA by qPCR test, and tumor response assessments until documented disease progression beyond 24-weeks of treatment, per modified WHO response criteria ([Appendix D](#)), until the start of a new anticancer therapy, or end of study, whichever the earliest. **Subjects treated for more than 24 months after the last subject is enrolled will not enter long-term follow-up (ie, their last visit will be the safety follow-up).**

^f Baseline blood for viral hepatitis testing will be collected at screening for reactive testing as required during the course of the study. Testing is not required for enrollment into the study.

^g If subject discontinues talimogene laherparepvec for a reason other than disease progression or death, tumor measurements are to be performed at the safety follow-up visit (if not performed within previous 4 weeks [+ 1 week]) and every 12 weeks (+ 1 week) during the long-term follow-up period until PDr beyond 6 months of treatment (per modified WHO response criteria as described in [Appendix D](#)) or until the start of a new anticancer therapy. **Long-term follow-up is not applicable for subjects treated beyond 24 months after the last subject is enrolled.**

^h The tumor assessment, physical exams, and ECOG performance status will be completed after 12 (\pm 1) weeks on treatment (ie, day 1 of week 11), and then every 12 (\pm 1) weeks (eg, weeks 23, 35, 47 etc.), or more frequently if clinically indicated, until PDr beyond 6 months of treatment (per modified WHO response criteria [see [Appendix D](#)]) or until the start of a new anticancer therapy.

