1. OBJECTIVES

1.1 Primary

There are 2 fold purposes for this study. 1 is to evaluate safety and tolerability and the other is to study the anti-tumor effects of talimogene laherparepvec in Japanese patients with unresectable stage IIIB-IV malignant melanoma.

- To evaluate the safety and tolerability of talimogene laherparepvec, subjects will be assessed by incidence of dose limiting toxicities (DLTs).
- These subjects will also be evaluated for the anti-tumor activity of talimogene laherparepvec as assessed by durable response rate (DRR) using modified World Health Organization (WHO) response criteria. DRR is defined as the rate of objective response (Complete response [CR] or partial response [PR]) lasting continuously for ≥ 6 months and starting any time within 12 months of initiating therapy.

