The efficacy of talimogene laherparepvec in subjects with regionally and distantly metastatic melanoma was evaluated in a pivotal, controlled, phase 3 study (Study 005/05) and a supportive, single-arm, phase 2 study (Study 002/03). Talimogene laherparepvec up to 4.0 mL 10^6 PFU/mL was administered at day 1, followed by dose of up to 4.0 mL of 10^8 PFU/mL 3 weeks later and then every 2 weeks. The phase 2 study was a single arm study conducted in 50 patients with unresectable late stage III or stage IV melanoma (Senzer et al, 2009). The overall response rate was 28%. More than half of the responses were complete and many were durable, with the majority lasting longer than 6 months. An important finding was that transient locoregional or distant progression, including new lesions, sometimes preceded response. In the open-label, randomized, phase 3 study of talimogene laherparepvec versus subcutaneously administered GM-CSF in stages IIIB, IIIC, and IV unresectable melanoma, talimogene laherparepvec or GM-CSF was administered until CR, clinically significant disease progression, intolerable side effects, 12 months of therapy without an objective response, or withdrawal of consent (Study 20110263; OPTiM). The primary endpoint of the study was durable response rate (objective response is maintained for at least 6 months). Primary analysis of the OPTiM Study showed a statistically significant difference between the rate of durable response among subjects treated with talimogene laherparepvec (16%; 95% CI: 12%, 21%) versus those treated with GM-CSF (2%; 95% CI: 0%, 5%) (p-value < 0.0001). Overall response rate was also improved from 6% with GM-CSF to 26% with talimogene laherparepvec (P < 0.0001, descriptive).

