7.2.4.2 Long-term Follow-up

All subjects who permanently discontinue talimogene laherparepvec for any reason other than withdrawal of full consent or death will be contacted by telephone, or clinic visit, to assess survival status and, if applicable, commencement of any subsequent anticancer melanoma therapy. Adverse events deemed by the investigator to be potentially related to talimogene laherparepvec and use of anti-cancer therapies for melanoma will also be recorded. Follow-up will occur every 12 weeks (\pm 28 days) following the safety follow-up visit until death, subject withdraws full consent, or up to 24 months after the last subject is enrolled in the study. **If a subject discontinues therapy more than 24 months after the last subject was enrolled in the study, when the long-term follow-up period ends, they will not enter long-term follow-up.** If a subject has discontinued talimogene laherparepvec for reason other than disease progression or death, radiographic tumor imaging, clinical tumor assessments, ECOG Performance Status assessments, reporting of pregnancy or lactation, assessment of swabs of lesions of suspected herpetic origin for presence of talimogene laherparepvec DNA by qPCR test, and tumor response assessments will be performed until documented disease progression beyond 24-weeks of treatment, per modified WHO response criteria ([Appendix D](#)), until the start of a new anticancer therapy, or end of study, whichever the earliest.

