The subject response will be assessed based on the response of the index lesions and nonindex lesion, and presence or absence of new lesions. Confirmation of complete or partial response is not required. The overall response is derived from time point response assessments as described in [Table 5](#), [Table 6](#) and [Table 7](#).

Table 5. Definition of Index Lesion Tumor Response Including New Lesions

Complete Response (CR):	Complete disappearance of all index lesions, including any new tumors which might have appeared. Any residual cutaneous or subcutaneous index lesions must be documented by representative biopsy to not contain viable tumor.
Partial Response (PR):	Achieving a 50% or greater reduction in the SPD of the perpendicular diameters of all index lesions at the time of assessment as compared to the sum of the products of the perpendicular diameters of all index lesions at baseline. If any new lesions have appeared, the sum of products of the perpendicular diameters of new measurable lesions must have reduced by 50% or more from when first documented. Any residual cutaneous or subcutaneous index or new lesions that must be tumor free for the subject to meet the criteria for PR must be documented as such by representative biopsy.
Disease Progression (PD):	A > 25% increase in the sum of the products of the perpendicular diameters of all index tumors since baseline, or the unequivocal appearance of a new tumor since the last response assessment time point. There are 2 types of PD defined in this protocol: Non-clinically relevant disease progression (PDn): PD in subjects who do not suffer a decline in performance status and/or in the opinion of the investigator do not require alternative therapy. Subjects showing overall response as PDn will be allowed to continue study treatment. Clinically relevant disease progression (PDr): PD that is associated with a decline in performance status and/or in the opinion of the investigator the subject requires alternative therapy. Subjects with PDr will be allowed to remain on study until 24 weeks of therapy unless, in the opinion of the investigator, other treatment is warranted.
Stable Disease (SD):	Neither sufficient tumor shrinkage of index lesion to qualify for response (PR or CR) nor sufficient tumor increase of index lesion to qualify for PD.

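### The protocol gives two end points for off-treatment tumor assessments, any progression beyond 24 weeks or PDr beyond 6 months; read literally, the first could miss a late durable response in a few subjects.

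*Protocol*

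**What the plan says.** Two rules cover the same subjects and the same assessments. Footnote e defines the group: "For subjects that discontinue talimogene laherparepvec for reason other than disease progression or death". Footnote g and Sections 7.3.14.1 and 7.3.14.2 describe it in equivalent words.

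- **Rule A** (Protocol Table 2 footnote e; Section 7.2.4.2). Footnote e requires "tumor response assessments until documented disease progression beyond 24-weeks of treatment, per modified WHO response criteria", and the section says "tumor response assessments will be performed until documented disease progression beyond 24-weeks of treatment". New anticancer therapy and end of study are the other stopping events, and the earliest one applies.
- **Rule B** (Table 2 footnote g; Sections 7.3.14.1 and 7.3.14.2). Measurement continues every 12 weeks "during the long-term follow-up period until PDr beyond 6 months of treatment", or until new anticancer therapy. End of study is not listed. Footnote h applies the same PDr criterion on treatment.

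On the meaning of progression, Appendix D states: "There are 2 types of PD defined in this protocol". These are PDn (no decline in performance status and/or no need for other therapy in the investigator's opinion) and PDr (clinically relevant). The primary efficacy endpoint counts an objective response "lasting continuously for ≥ 6 months and starting any time within 12 months of initiating therapy".

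**The concern.** A PDn after week 24, such as a new lesion in a subject who is otherwise well and needs no other therapy, ends tumor assessments under Rule A but not under Rule B. The protocol itself expects some responses to follow progression. Section 2.2 reports from the phase 2 study that "transient locoregional or distant progression, including new lesions, sometimes preceded response", and Appendix D Table 5 allows a PR after new lesions have appeared, provided the measurable ones shrink by at least half.

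The DRR definition does not exclude a response that begins after a progression. If measurement has stopped, such a response cannot be recorded and the subject counts as not durable. Data collection for a primary endpoint would then depend on which footnote a site follows, in a trial whose test turns on 2 responders out of 18.

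**Working it through.** **1. The plan's own figures.** Inputs from Protocol 10.2.1.2 and SAP Table 2: n = 18, reject at 2 or more durable responders, null DRR 2%, alternative 16.3%.

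- Significance level: 1 − 0.98^18 − 18 × 0.02 × 0.98^17 = 1 − 0.6951 − 0.2554 = 0.0495. The SAP states 5.0%.
- Power: 1 − 0.837^18 − 18 × 0.163 × 0.837^17 = 1 − 0.0406 − 0.1425 = 0.8169. The protocol states 81% and the SAP 81.7%.

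The design reproduces.

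**2. The two rules side by side.**

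| | Footnote e; 7.2.4.2 | Footnote g; 7.3.14.1; 7.3.14.2 |
|---|---|---|
| Progression that ends assessment | PD of either type | PDr only |
| Time limit | 24 weeks | 6 months |
| Other stopping events | New therapy, end of study | New therapy |

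**3. Is the time limit the material difference?** 24 weeks is 168 days and 6 months is about 183 days, a gap of about 15 days. On the on-treatment calendar (footnote h), the week 23 (±1) assessment falls on days 154–168 and the week 35 (±1) assessment on days 238–252. Neither lies between day 168 and day 183, so both limits pick out the same scheduled scan. An unscheduled scan, or a follow-up calendar shifted by the safety visit, could fall in the gap. The material difference is PD of either type against PDr.

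**4. Can a durable response be lost?** Take a subject whose last dose is at week 27 (27 × 7 = 189 days after the first), who stops for a reason other than progression. Treatment has then passed both limits.

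- Safety visit: 189 + 30 = day 219, about week 31. Footnote g requires a scan, because the week 23 (±1) scan is more than 5 weeks old. Suppose it shows PDn.
- Next 12-weekly scan: 219 + 84 = day 303, about week 43. Suppose it shows PR. This is before day 365, so the response starts in the window.
- Later scans at days 387, 471 and 555. Day 471 is only 168 days after day 303. Day 555 is 252 days after it and is the first scheduled scan to show at least 6 months.

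Under Rule B this subject can be counted as a durable responder. Under Rule A, tumor assessment ends at about week 31. The path is narrow: if the PDn were first seen at week 43, this subject's next scheduled scan would be day 387, after the 12-month window has closed.

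**5. What one missed responder costs.** Observed DRR changes by 1/18 = 5.6 percentage points. The test result changes only if the true count is exactly 2. At a DRR of 16.3%, P(X = 2) = 153 × 0.163² × 0.837^16 = 0.236.

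**6. Illustration of lost power.** The documents give no share of durable responders lost. With an assumed share m, the observable DRR is 0.163 × (1 − m):

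| Assumed share lost | Observable DRR | Power |
|---|---|---|
| 0% | 16.3% | 81.7% |
| 5% | 15.5% | 79.2% |
| 10% | 14.7% | 76.4% |
| 20% | 13.0% | 70.1% |

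These shares are assumptions that show the scale. They are not estimates.

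**The case against.** The strongest reply is that footnote e is shorthand for PDr. In Table 2 the follow-up cells of both tumor-assessment rows carry footnote g, while footnote e sits on the long-term follow-up column and lists several unrelated procedures. Section 7.2 sends the reader to later subsections for procedural detail, and both tumor-assessment subsections say PDr. The treatment-stopping text in the synopsis and Sections 3.5.1, 6.2.1.1 and 6.2.2 uses a similar phrase with the clinically-relevant qualifier. In Appendix D the 24-week limit is attached only to PDr. A dropped qualifier is therefore a plausible explanation.

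Most of this stands, and it makes PDr the likely intention. It does not settle the text. Section 7.2.4.2 is itself one of the later subsections and repeats the unqualified wording. Elsewhere the protocol adds the qualifier when it means clinically relevant progression. No passage gives one rule precedence.

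It is also fair to say that the affected group is narrow. The subject must stop for a reason other than progression, then have an off-treatment PDn after the time limit without starting new therapy, then begin a response by month 12 and hold it for 6 months. A PDn during an ongoing response already breaks continuity under either rule. Subjects who stopped because of progression get no further protocol tumor assessments under either footnote, so reconciling the text does not help them.

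A reader might infer a 23.6% chance that the trial's conclusion is reversed. The documents do not support that. The figure is the probability of exactly 2 durable responders. Harm also requires that one of those two followed this path, and that probability is unknown and probably small.

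**Conclusion.** The inconsistency is real. It lies within Table 2 and is repeated in the body text, so it is not a single misplaced word. Followed literally, footnote e and Section 7.2.4.2 would stop measurement in a subject who can still meet the primary efficacy endpoint.

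The size is limited. Only a response that begins after an off-treatment PDn is at risk, and the documents do not say how many subjects that could be. Each one missed costs 5.6 points of observed DRR and reverses the test only at a true count of exactly 2. ORR and TTR could miss the same response if the subject had not responded earlier. PFS is unaffected, because the SAP counts progression of either type as the event.

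Two stronger conclusions would be wrong. The direction is downward, which is conservative against the 2% null, so type I error is not inflated. The difference between 24 weeks and 6 months has little effect on scheduled scans.

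The conclusion rests on Appendix D's division of progression into two types and on reading footnote e as written.

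**What to change.** In Table 2 footnote e and Section 7.2.4.2, replace the unqualified progression wording with the PDr criterion already used in footnotes g and h and Sections 7.3.14.1 and 7.3.14.2. Across all six places, state one time limit (24 weeks or 6 months) and one list of stopping events, including whether end of study is one of them. Say what the time limit is counted from, because its meaning is unclear for a subject who stops dosing before reaching it.

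The cost is a wording change in a protocol amendment. Sites would do no assessments beyond those footnote g already requires.
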